12.4.2 Videonystagmography (VNG)

Participants will be asked to wear a goggle-like device that is equipped with a camera to track the pupils of the eye. Participants will be instructed to keep their eyes wide open and gaze ahead or on a specific target. Following this, participants will then be asked to lie in a supine position where they will be rolled to each side by the examiner whilst tracking the eye movements.

12.4.3 Audiometry

Formal testing of air and bone conduction hearing thresholds will be undertaken using a laptop-based audiometer. This test is designed to measure hearing acuity by a variation of tones in pitch and sound intensities played through a set of headphones. This test will be performed in a quiet room.

12.4.4 Otoacoustic Emissions test

Measures the otoacoustic emissions (OAEs) produced by the outer hair cells of cochlea as part of the pre-neural active process within the cochlea. Otoacoustic emissions can occur spontaneously or they can be elicited by presenting sound into the ear canal. The test is performed by inserting a foam earbud tip into the ear and a distortion product tone or broadband click will be played to elicit this response. Otoscopy and tympanometry will be performed before to test middle ear integrity as middle ear dysfunction is contraindicated in this test as it will not produce a response.

12.4.5 Video head impulse test (VHIT)

Measures the vestibular function through testing the vestibulo-ocular reflex. The participants will wear lightweight goggles which will track eye and head movement concurrently using a high speed camera and a motion sensor in the goggles whilst the participant is viewing a target at eye level 1.5 metres away. The examiner firmly holds the participant's head and delivers brief, unpredictable, low amplitude (10-20 degrees) and high velocity (150-300 degrees/s) head movements in the plane of the 3 pairs of semicircular canals. Head and eye velocity are measured and displayed in real time. For each semicircular canal tested, in the presence of an intact vestibulo-ocular reflex (VOR), each head impulse generates an equal and opposite eye movement and the "gain" of the angular VOR in this canal plane (eye velocity/head velocity) is close to 1. Three dimensional video head impulse testing includes assessment of the angular VOR in all 6 semicircular canal planes. The VHIT quantifies dysfunction of semicircular canals.

12.4.6 Vestibular Evoked Myogenic Potential (VEMP)

Measures vestibular function through activating the otolith organs in the ear to elicit "vestibular evoked myogenic potentials". Cervical and ocular vestibular evoked myogenic potentials (cVEMP and oVEMP respectively) are two tests which will be performed together. The participant will have EMG electrodes placed on the face and the neck whilst in a supine position.

i) Cervical Vestibular evoked myogenic potential (cVEMP): Measures the functionality of the saccule by activating a myogenic potential through playing sound through headphones. To ensure proper contraction of the muscle participants will be instructed to lift their head and turn to each side. This produces a muscle reaction in the sternocleidomastoid muscle which is recorded through the EMG electrodes.

ii) Ocular Vestibular evoked myogenic potentials (oVEMP): Measures the functionality of the utricle which is activated through tone bursts/vibrations against the participant's forehead using a 'mini shaker' oscillator (like gentle tapping on centre of forehead). The

participant will be asked to look up as far as possible with their eyes as the oscillator is vibrating against the forehead.

12.5 Psychological and psychiatric health

The following questionnaires will be measured baseline and at three months and six months (see Appendix B)

Baseline and 3 month and 6 month outcomes:

1. Noise Annoyance Scale
2. Symptom Visual Analogue Scales
3. Warwick Edinburgh Mental Well-being Scale (WEMWBS)
4. Depression Anxiety and Stress Scale (DASS-21)
5. Insomnia Severity Index (ISI)
6. EYSENCK Questionnaire
- Attitudes on Wind farms⁸. Kessler (10)
9. Depression Anxiety Stress Scale (DASS-21)

12.6 General health assessment

Anthropometric measurements such as height, weight, waist circumference and the blood pressures of each arm will be taken at the face to face home screening visit and the baseline, 3 month and six month outcome assessment visits.

12.7 Polysomnography (PSG) (Appendix F)

Home-based polysomnography (PSG) for assessment of sleep and sleep quality will include multichannel recording including oximetry, ECG, EEG, EMG, flow and chest and abdomen movement using a small portable recorder (Alice PDx, Philips Respironics). A sleep scientist will attach equipment in the late afternoon and retrieve it in the morning. Polysomnography data will be analysed by a single core laboratory at the Woolcock Institute of Medical Research (The University of Sydney, NSW, Australia) using standardised analysis and reporting protocols.

12.8 Neurocognitive Assessments

The computerised neurocognitive test battery will include the N-back and the Tower of London test. Neurocognitive tests will occur at baseline, three and six month clinical assessments.

12.8.1 N-back (2-back) (5 mins)

This test involves the participant monitoring a series of stimuli and requires them to respond whenever a stimulus is presented that is the same location as the one presented n trials previously, where n is a pre-specified integer, usually 1, 2, or 3. The task requires on-line monitoring, updating, and manipulation of remembered information and is therefore assumed to place great demand on a number of key processes within working memory.

12.8.2 Tower of London (3-5min)

This computerised test involves the presentation of two different arrangements of coloured balls on the monitor. The subject's task is to rearrange the first array of balls so that it matches the second array of balls using the minimum number of moves possible with the mouse. The positioning of the balls is constrained to the location of three pegs in each display. This test demands that the sequence of moves is carefully planned in advance before attempting the first move. Failure to engage in advanced planning of the sequence will result in initial moves blocking subsequent ball moves. This test involves using "executive" function, specifically forward planning, to solve a problem. Accuracy, determined as the number of moves, and speed, using time, variables can be obtained.

12.9 Cardiovascular and stress measures (Appendix H)

12.9.1 Pulse wave Velocity (10-15 minutes)

Pulse Wave velocity is the gold standard for measuring for aortic stiffness. The measurement is a painless, non-invasive test and entails inflating a cuff around a fully clothed thigh whilst simultaneously placing a pressure probe on the carotid artery of the neck across the skin. The test will require the participant to maintain a resting period of 10 minutes and 5 minutes measuring periods. This measurement will be recorded whilst in the exposure of the experimental noise conditions.

12.9.2 Heart rate variability

This will be measured through ECG leads which are attached during routine overnight sleep study. This will be analysed using PRANA[®] Software Suite.

12.9.3 Blood test for inflammatory markers

A blood sample will be taken on the last morning of each lab stay using standard venepuncture technique to measure inflammatory markers including: highly sensitive CRP, interleukin (IL)-6, TNF-alpha and HbA1c. Over the 3 clinical assessments a total blood volume of 130mL will be taken from each participant which is less than one routine blood donation (~400mL). Approximately, 40mL of blood will be taken from the arm at each visit. Three 8.5mL gold serum separating tubes and one 4mL purple EDTA will be sent to a local pathology laboratory and an extra two 8.5mL gold serum separating tubes will be centrifuged and the serum will be extracted and stored at -80°C at the Woolcock Institute.

12.10 Insomnia Severity Index (ISI) questionnaire (see Appendix B)

The ISI is a 7-item patient reported outcome measure that probes the severity of both the night time and daytime impact of insomnia and takes approximately 3 minutes to complete. Each item uses a 5-point Likert scale to capture a rating (0 = no problem; 4 = very severe problem) which add up to: no insomnia (0 – 7); sub-threshold insomnia (8 – 14); moderate insomnia (15 – 21); and severe insomnia (22 – 28). It will be completed at baseline, three and six month clinical assessments.

13. Data Management

All data will be collected in the home in written and computerised formats. Paper records shall be securely stored in locked cabinets at the Woolcock Institute of Medical Research for up to 15 years following the end of the study. Computerised data will be stored and backed-up on a secure cloud based, individual password protected database system (Research Tools™) which logs all access or changes to data back to individual users who will be given only access or change privileges to data which they require for their role. During data collection, only investigators named at the front of this protocol, the unblinded study statistician and the data safety monitoring committee will be allowed access to the study data under the supervision of the Principal Investigators. After study completion, a non-identifiable dataset (does not include information that could help identify a participant such as date of birth, address or ethnicity) may be published in an open access data repository. All data will be re-identifiable as, once randomised into the study, participants will be allocated an individual study code number. The master coding sheet will be kept in a password encrypted file and only investigators and research staff will have access to it. However, if needed, each individual will be able to be re-identified.

14. Statistical Methods

Generalised linear mixed models will be utilised for statistical analysis. WASO will be the dependent variable in the primary analysis. All other outcomes will be tested separately as dependent variables. Exposure (infrasound vs sham) will be the main fixed effect. As multiple outcome measures will be made (at baseline and at 3 & 6 month follow-ups) a “time” fixed effect will also be included and exposure-by-time interactions will be tested. The differences specifically at the 6 month time period will be the primary endpoint. In sub-analyses we will also test whether changes in outcomes are influenced by whether people thought windfarms have health effects (expectancy) to establish whether this attribute modifies the propensity to experience WTS symptoms with exposure

15. Methods: Monitoring

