6.1 Discontinuing

Withdrawal criteria

Participants will be informed that they have the right to withdraw from the study at any time, without prejudice to any medical care (such that might be required if we incidentally identify a medical condition), and are not obliged to state their reasons. Additionally the investigator may withdraw a participant at any time for the following reasons:

- If any of the study exclusion criteria are diagnosed
- Protocol violations
- Adverse events

Discontinuation of the study

The study may be discontinued at any time on the advice of the responsible principal investigators on the basis of new information regarding safety. A Data Safety Monitoring Board has been constituted to provide advice to the investigator team with regard to participant safety (Section 15.1). Additionally, the study may be terminated if progress is unsatisfactory.

In the case of premature termination or suspension of the experiment, the investigator will inform the study participants and ensure appropriate follow up in the unlikely event this is required clinically. In addition, the appropriate ethics committee will be informed.

Procedure to withdraw

Participants with clinically significant abnormalities requiring discontinuation will be followed until recovery from the abnormality. If the study is discontinued for safety reasons, the investigators will contact all affected participants within a week to inform them of the termination of their involvement in the study. Participants discontinuing from the study may be replaced. A new participant number must be issued for the new participant.

If a participant fails to respond to telephone contact or is consistently unavailable for home visit, attempts will be made to ensure that the reason for not communicating is not an adverse event (bearing in mind that the participant is not obliged to state his/her reasons).

7. Outcomes

Primary outcome measure:

Changes in wake after sleep onset (WASO) as determined by 4 EEG channel polysomnography with portable recorder at baseline, 3 and 6 months. We will compare the differences between infrasound and sham sound.

Secondary outcome measures:

EEG parameters from the overnight sleep studies - Sleep latency, sleep staging, sleep stage shifts, arousal frequency and power spectral analysis for sleep microarchitecture analysis.

Tertiary Outcome Measures:

Neurocognitive tests (Section 12.8):

N-back

Tower of London

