8.4 Reimbursement

Participants will be fully reimbursed for the additional cost of electricity for running the speakers and microphones. We anticipate that this amount will be in the range of \$60 to \$120. We will offer a payment of \$1,000 to cover electricity and the inconvenience of having the speakers in the home and participating in the testing for all participants involved in this study.

9. Sample size

From previous studies, the between-subject standard deviation in wake after sleep onset (WASO) is conservatively estimated at 20 minutes. Most trials of treatments for insomnia, for instance, regard a change of 15 minutes or more in WASO as being clinically meaningful. A sample size of 120 participants (which includes allowance for 22 dropouts) will have 85% power to detect a 0.25 effect size (Cohen's f).

10. Recruitment

Number and source of participants

The target number of participants is 120. This will provide 60 participants in the infrasonic group and 60 participants in the sham group.

Participants will be found by public advertising in local newspapers, community radio, television media and social media through the Woolcock website and its database of

research volunteers which will direct all volunteers to the online screening website (Appendix A).

11. Methods: Assignment of interventions

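### Section 14 leaves baseline WASO unadjusted and unconstrained across arms, so the month-6 contrast is less precise than the collected data allow

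*Protocol*

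**What the plan says.** Section 14 (Statistical Methods) specifies generalised linear mixed models with WASO as the dependent variable. "Exposure (infrasound vs sham) will be the main fixed effect". The repeated measures include the baseline visit: "As multiple outcome measures will be made (at baseline and at 3 & 6 month follow-ups"). A time effect and exposure-by-time interactions are added, and the difference at 6 months is named as the primary endpoint. The section mentions no baseline covariate and no equality of baseline means between arms.

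Section 7 (Outcomes) words the primary outcome as change: "Changes in wake after sleep onset (WASO) as determined by 4 EEG channel polysomnography with portable recorder at baseline, 3 and 6 months".

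Section 8.3 has the speakers installed after baseline testing is complete, so the baseline visit is pre-exposure.

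Sections 9 and 10 supply the design figures. "A sample size of 120 participants (which includes allowance for 22 dropouts") "will have 85% power to detect a 0.25 effect size (Cohen's f"). Also: "This will provide 60 participants in the infrasonic group and 60 participants in the sham group", and "the between-subject standard deviation in wake after sleep onset (WASO) is conservatively estimated at 20 minutes".

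**The concern.** Under randomisation, with speakers installed only after baseline testing, the arms share the same expected baseline WASO. A model that gives each arm its own mean at every visit ignores this. Its month-6 contrast is then, with complete data, the plain difference in month-6 means, and baseline WASO contributes nothing. The other natural reading, suggested by the word for change in Section 7, is the exposure-by-time contrast from baseline to month 6. That does use baseline, but it subtracts it with a coefficient of 1 instead of the regression coefficient, which adds noise unless the visits are very highly correlated.

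What is at stake is precision. A null result from this trial would be read as reassurance about infrasound, so the width of the interval matters as much as the p-value. Under the raw-difference reading, a chance imbalance in baseline WASO would also carry over, in proportion to the between-visit correlation, into the month-6 comparison. The two sections also leave open which of the two contrasts is meant, and the contrasts have different power.

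**Working it through.** **Inputs from the protocol.** 120 randomised, 60 per arm; 22 dropouts allowed for, leaving 98, or 49 per arm; SD 20 min. Cohen's f = 0.25 for two groups is d = 2 × 0.25 = 0.50, or 0.50 × 20 = 10 min. The difference described as clinically meaningful is 15 min (d = 0.75).

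**Assumptions, because the protocol does not state them.** Two-sided alpha 0.05; equal SD at each visit; a common between-visit correlation ρ, shown over 0.3 to 0.7.

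**The protocol's own 85%.** A single-visit comparison of 49 per arm at d = 0.50 has 69% power, not 85%. A between-group F test averaged over m visits has noncentrality λ = f²·N·m / (1 + (m − 1)ρ).
- m = 3, ρ = 0.5: λ = 0.0625 × 98 × 3 / 2 = 9.19, power 85.1%.
- m = 2, ρ = 0.5: power 80.8%.
- m = 2, ρ = 0.3: power 86.0%.

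So 85% can be reproduced as a pooled test over three visits, but two visits at a lower correlation come close. The match does not show which was used.

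**Variance of the month-6 contrast** relative to the raw difference, complete data:
- raw month-6 difference: 1
- change from baseline: 2(1 − ρ)
- baseline-adjusted (covariate or common baseline mean): 1 − ρ²

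SE = 20 × √(2 × factor / 49). For the raw difference this is 20 × √(2/49) = 4.04 min. Power is from the noncentral t with 96 df, for a 10-min difference.

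| ρ | raw: SE, power | change: SE, power | adjusted: SE, power |
|---|---|---|---|
| 0.3 | 4.04, 69% | 4.78, 54% | 3.85, 73% |
| 0.5 | 4.04, 69% | 4.04, 69% | 3.50, 81% |
| 0.6 | 4.04, 69% | 3.61, 78% | 3.23, 86% |
| 0.7 | 4.04, 69% | 3.13, 89% | 2.89, 93% |

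For any ρ between 0 and 1, 1 − ρ² is below 1, and its ratio to 2(1 − ρ) is (1 + ρ)/2, also below 1. Adjustment is therefore more precise than either alternative throughout. At ρ = 0.5 the variance falls by 25%, equivalent to 1/0.75 = 1.33 times the participants.

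A generalised least squares check with three visits and a common baseline mean gave the same SEs as adjustment: 3.85, 3.50 and 2.89 at ρ = 0.3, 0.5 and 0.7.

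**Allowing for dropouts.** With 60 baselines and 49 month-6 values per arm, a likelihood mixed model with free arm means borrows a little from the dropouts' baselines. At ρ = 0.5 the SE falls from 4.04 to 3.95 and power rises to about 71%.

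**At 15 minutes.** The raw difference has about 96% power, and the adjusted one about 99% at ρ = 0.5.

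**Pooled exposure effect.** If the true differences are 0, 10 and 10 min at baseline, 3 and 6 months, the exposure effect averaged over the three visits is (0 + 10 + 10)/3 = 6.67 min, two thirds of the post-installation difference. Its SE at ρ = 0.5 is 20 × √(2 × (2/3) / 49) = 3.30 min, and its power about 52%.

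**The case against.** The strongest reply is that Section 14 is an outline. It excludes neither a baseline covariate nor a common baseline mean, and an analysis plan not shown here could add either. Keeping baseline in the outcome vector is not a fault in itself, since the constrained model does so too. This stands as a limit. What remains is that the terms the protocol does list lead, as written, to one of two less precise contrasts, and that Sections 7 and 14 point to different ones.

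A reader might infer that the pre-installation visit dilutes the primary result. The documents do not support that. The named endpoint is the month-6 difference, which gives no weight to the baseline difference. Calling exposure the main fixed effect may only mean that it is the principal factor, and no pooled exposure test is declared primary. Nor does the 85% figure prove that baseline was pooled, as the two-visit calculation shows.

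A reader might also infer that baseline goes wholly unused, or that the estimate is biased. Neither holds. The change contrast uses baseline, the mixed model recovers a little from dropouts, and both contrasts are unbiased under randomisation.

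Finally, the gain depends on a correlation that the protocol does not give. At 0.3 it is only 4 percentage points over the raw difference. At 0.6 it is 8 points over the change contrast. At 15 minutes the raw contrast is already well powered.

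**Conclusion.** The point holds as one of efficiency and clarity. Neither reading of the month-6 contrast makes the best use of a baseline measurement that is scheduled for every participant. For the 10-minute difference used in sizing, adjustment raises power from about 69% (raw; about 71% using dropouts' baselines at ρ = 0.5) to between 73% and 93% for ρ from 0.3 to 0.7. Over the same range the change contrast runs from 54% to 89%. These figures rest on two-sided alpha 0.05, 49 completers per arm, SD 20 minutes at each visit, and an assumed ρ. There is no bias in the month-6 contrast and no dilution of it. The two-thirds dilution applies only to an exposure effect pooled over all three visits, which should be ruled out explicitly as a test of effect.

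**What to change.** In Section 14, with matching wording in Section 7, name one primary test: the month-6 infrasound-minus-sham difference in WASO, obtained in one of two ways.

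- **Constrained form:** a mixed model of baseline, 3- and 6-month WASO with baseline means constrained equal across arms.
- **Covariate form:** a mixed model of the 3- and 6-month values with baseline WASO and its interaction with time as covariates.

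Add a sentence that the exposure effect pooled over visits including baseline is not a test of effect.

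The cost is a few words and small code changes, with no new data or participants. The covariate form needs a rule for participants whose baseline PSG is missing or failed; the constrained form avoids this. If the change is made as a protocol amendment, Section 19 requires submission to the ethics committee and further consent.

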15.1 Data monitoring

Because infrasound like this has not been used in experiments of longer than 2 hours duration a Data Safety Monitoring Board has been convened. The DSMB will oversee participant safety in both the laboratory study (Protocol No X16-0073 & HREC/16/RPAH/91) and this community based study by reviewing unblinded accumulated safety data pertaining to infrasound.

16. Adverse Events Reporting

Collection of adverse events will occur throughout the study.

Serious adverse events (SAE) are defined as any untoward medical occurrence that:

- Results in death
- Is an immediately life-threatening condition
- Requires hospitalisation or prolongs hospitalisation
- Results in persistent or significant disability/incapacity
- Is a congenital anomaly/birth defect
- Results in any other important medical condition.

The Ethics Committee will be notified of any SAE within 72 hours.

17. Auditing

The study will not be externally audited

18. Ethics and dissemination

18.1 Study conduct/ethics approval

The study will be conducted under the ethical jurisdiction of the Sydney Local Health District (SLHD) Ethics Committee at Royal Prince Alfred Hospital and will be performed in accordance with the Declaration of Helsinki,²⁷ the Australian Good Clinical Research Practice Guidelines²⁸ (Commonwealth of Australia, 1991) and the guidelines of the National Health and Medical Research Council for human research.²⁹

19. Protocol amendments

Any amendments to the protocol will be made in writing to the SLHD Ethics Committee after discussion with all co-investigators, and then be communicated to all participants, whereby further consent will be obtained for any protocol amendments.

20. Confidentiality

Participant data will be identified by a code number that will be allocated after the participant gives consent to participate in the study. The key linking the participant's identity to the relevant code will be stored in a password encrypted file that will not be accessible from the internet. Storage of the data collected will adhere to the University regulations & the Australian Code for the Responsible Conduct of Research. A dataset containing individual participant data will be published online in conjunction with the academic publication of these data. That dataset will be non-identifiable and will not contain any personal information about the participant that could be used to identify them (including age, gender, ethnicity, address or postcode). In any publication and/or presentation, information will be provided in such a way that participants cannot be identified, except with their written, informed permission. Any information obtained for the purpose of this research that could identify participants will be treated as confidential and securely stored.

21. Declaration of Interests

None of the investigators have any pecuniary interest or academic conflict of interests in the outcomes of this study.

22. Access to data

During the study only investigators and members of the study team will have access and control to any data collected from participants. There are no contractual agreements that would limit access or control of the study to the investigators. After the study, a non-identified dataset will be made available online in a data repository. Making data available in such a way is increasingly becoming an expectation of research teams who conduct publicly funded research.

23. Ancillary and post-trial care

As this is not a clinical trial for a medical condition and does not involve any treatment, no clinical follow up will be routinely offered to participants. If however any harm is caused during this protocol or a medical condition becomes apparent, then medical follow-up will be arranged with either a member of the clinical research team or the participant's normal medical practitioner.

24. Dissemination policy

Study results will be published in peer-reviewed journals and participants will be made aware of these following publication should they desire. The publication committee consists of [name] & [name], A/[name] and Drs [name] and [name]. They shall be responsible for the formulation and execution of publication plans. Authorship on any manuscripts will be at the discretion of the publication committee.

25. Appendix

B Questionnaires

I. Weinstein's Noise Sensitivity (WNS) Scale

Home In Lab Recruitment Screening Sign In

Back Save & Back

Weinstein Noise Sensitivity Score

AC Male 01/01/1977 1 Remove

1. I wouldn't mind living on a noisy street if the apartment I had was nice.
AGREE 1 2 3 4 5 6 DISAGREE

2. I am more aware of noise than I used to be
AGREE 6 5 4 3 2 1 DISAGREE

3. No one should mind much if someone turns up his stereo full blast once in a while
AGREE 1 2 3 4 5 6 DISAGREE

4. At movies, whispering and crinkling candy wrappers disturbs me
AGREE 6 5 4 3 2 1 DISAGREE

5. I am easily awakened by noise
AGREE 6 5 4 3 2 1 DISAGREE

6. If it's noisy where I'm studying, I try to close the door or window or move someplace else
AGREE 6 5 4 3 2 1 DISAGREE

7. I get annoyed when my neighbours are noisy
AGREE 6 5 4 3 2 1 DISAGREE

8. I get used to mose noises without much difficulty
AGREE 1 2 3 4 5 6 DISAGREE

9. How much would it matter to you if an apartment you were interested in renting was located across from a fire station
A LOT 6 5 4 3 2 1 NOT MUCH

10. Sometimes noises get on my nerves and get me irritated
AGREE 6 5 4 3 2 1 DISAGREE

11. Even music I normally like will bother me if I'm trying to concentrate
AGREE 6 5 4 3 2 1 DISAGREE

12. It wouldn't bother me to hear the sounds of everyday living from my neighbours (footsteps, running water etc.)
AGREE 1 2 3 4 5 6 DISAGREE

13. When I want to be alone, it disturbs me to hear outside noises
AGREE 6 5 4 3 2 1 DISAGREE

14. I'm good at concentrating no matter what is going on around me
AGREE 1 2 3 4 5 6 DISAGREE

15. In a library, I don't mind if people carry on a conversation if they do it quietly
AGREE 1 2 3 4 5 6 DISAGREE

16. There are often times when I want complete silence
AGREE 6 5 4 3 2 1 DISAGREE

17. Motorcycles ought to be required to have bigger mufflers
AGREE 6 5 4 3 2 1 DISAGREE

18. I find it hard to relax in a place that's noisy
AGREE 6 5 4 3 2 1 DISAGREE

19. I get mad at people who make noise that keeps me from falling asleep or getting work done
AGREE 6 5 4 3 2 1 DISAGREE

20. I wouldn't mind living in an apartment with thin walls
AGREE 1 2 3 4 5 6 DISAGREE

21. I am sensitive to noise.
AGREE 6 5 4 3 2 1 DISAGREE

Copyright © 2016, Woolcock Institute of Medical Research

II. Insomnia Severity Index (ISI) questionnaire

Insomnia Severity Index					
select a participant...					Remove
For each question, please click on the number that best describes your answer.					
1. Please rate the CURRENT (i.e. LAST 2 WEEKS) SEVERITY of your insomnia problem(s).					
	None	Mild	Moderate	Severe	Very Severe
a. Difficulty falling asleep	0	1	2	3	4
b. Difficulty staying asleep	0	1	2	3	4
c. Problem waking up too early	0	1	2	3	4
2. How SATISFIED/DISSATISFIED are you with your CURRENT sleep pattern?					
	Very Satisfied	Satisfied	Neutral	Dissatisfied	Very Dissatisfied
	0	1	2	3	4
3. To what extent do you consider your sleep problem to INTERFERE with your daily functioning (e.g. daytime fatigue, mood, ability to function at work/daily chores, concentration, memory, mood, etc.) CURRENTLY?					
	Not at all Interfering	A Little	Somewhat	Much	Very Much Interfering
	0	1	2	3	4
4. How NOTICEABLE to others do you think your sleep problem is in terms of impairing the quality of your life?					
	Not at all Noticeable	A Little	Somewhat	Much	Very Much Noticeable
	0	1	2	3	4
5. How WORRIED/DISTRESSED are you about your current sleep problem?					
	Not at all Worried	A Little	Somewhat	Much	Very Much Worried
	0	1	2	3	4

Save & Back

III. Depression Anxiety and Stress Scale (DASS-21)

DASS - 21				
select a participant...				Remove

Please read each statement and click on a number 0, 1, 2 or 3 which indicates how much the statement applied to you over the past week. There are no right or wrong answers. Do not spend too much time on any statement.
				
	Did not apply to me at all	Applied to me to some degree, or some of the time	Applied to me to a considerable degree, or a good part of time	Applied to me very much, or most of the time
1. I found it hard to wind down	0	1	2	3
2. I was aware of dryness of my mouth	0	1	2	3
3. I couldn't seem to experience any positive feeling at all	0	1	2	3
4. I experienced breathing difficulty (eg, excessively rapid breathing, breathlessness in the absence of physical exertion)	0	1	2	3
5. I found it difficult to work up the initiative to do things	0	1	2	3
6. I tended to over-react to situations	0	1	2	3
7. I experienced trembling (eg, in the hands)	0	1	2	3
8. I felt that I was using a lot of nervous energy	0	1	2	3
9. I was worried about situations in which I might panic and make a fool of myself	0	1	2	3
10. I felt that I had nothing to look forward to	0	1	2	3
11. I found myself getting agitated	0	1	2	3
12. I found it difficult to relax	0	1	2	3
13. I felt down-hearted and blue	0	1	2	3
14. I was intolerant of anything that kept me from getting on with what I was doing	0	1	2	3
15. I felt I was close to panic	0	1	2	3
16. I was unable to become enthusiastic about anything	0	1	2	3
17. I felt I wasn't worth much as a person	0	1	2	3
18. I felt that I was rather touchy	0	1	2	3
19. I was aware of the action of my heart in the absence of physical exertion (eg, sense of heart rate increase, heart missing a beat)	0	1	2	3
20. I felt scared without any good reason	0	1	2	3
21. I felt that life was meaningless	0	1	2	3

Save & Back

IV. Visual Analogue Scale for Symptom

Back Save & Back

Visual Analogue Scale

select a participant... Remove

Residents living within the area of Wind turbines present with complaints of the following symptoms. After each symptom listed, please click along the line in which best describes your current state and symptom.

HEADACHE
Not at all  _____  Worst I can imagine
RINGING IN THE EARS
Not at all  _____  Worst I can imagine
ITCHY SKIN
Not at all  _____  Worst I can imagine
BLURRED VISION
Not at all  _____  Worst I can imagine
DIZZINESS
Not at all  _____  Worst I can imagine
RACING HEART
Not at all  _____  Worst I can imagine
VERTIGO
Not at all  _____  Worst I can imagine
NAUSEA
Not at all  _____  Worst I can imagine
TIREDNESS
Not at all  _____  Worst I can imagine
FEELING FAINT
Not at all  _____  Worst I can imagine
SLEEPINESS
Not at all  _____  Worst I can imagine
DIFFICULTY CONCENTRATING
Not at all  _____  Worst I can imagine
DIFFICULTY REMEMBERING
Not at all  _____  Worst I can imagine
FATIGUE
Not at all  _____  Worst I can imagine
IRRITABILITY
Not at all  _____  Worst I can imagine
MUSCLE SPASMS
Not at all  _____  Worst I can imagine
DISRUPTION WHILE FALLING ASLEEP
Not at all  _____  Worst I can imagine
AWAKENING FROM SLEEP
Not at all  _____  Worst I can imagine
ANXIETY
Not at all  _____  Worst I can imagine

We are also adding the following list of symptoms that are not typically associated with wind farm health complaints: stomach ache, sore jaw, hand tremble or shake.

V. Noise Annoyance Scale

Noise Annoyance Scale	
select a participant...	Remove
Please click along the line in which best describes your current annoyance with the noise.	
NOISE ANNOYANCE	
Not Annoyed	Very Annoyed

VI. Warwick Edinburgh Mental Well-being Scale

The Warwick-Edinburgh Mental Well-being Scale (WEMWBS)					
select a participant...					Remove
Below are some statements about feelings and thoughts.					
Please tick the box that best describes your experience of each over the last 2 weeks					
	None of the time	Rarely	Some of the time	Often	All the time
1. I've been feeling optimistic about the future	 1	 2	 3	 4	 5
2. I've been feeling useful	 1	 2	 3	 4	 5
3. I've been feeling relaxed	 1	 2	 3	 4	 5
4. I've been feeling interested in other people	 1	 2	 3	 4	 5
5. I've had energy to spare	 1	 2	 3	 4	 5
6. I've been dealing with problems well	 1	 2	 3	 4	 5
7. I've been thinking clearly	 1	 2	 3	 4	 5
8. I've been feeling good about myself	 1	 2	 3	 4	 5
9. I've been feeling close to other people	 1	 2	 3	 4	 5
10. I've been feeling confident	 1	 2	 3	 4	 5
11. I've been able to make up my own mind about things	 1	 2	 3	 4	 5
12. I've been feeling loved	 1	 2	 3	 4	 5
13. I've been interested in new things	 1	 2	 3	 4	 5
14. I've been feeling cheerful	 1	 2	 3	 4	 5

[Save & Back](#)

C. Online Screening- Ethnicity, Lifestyle, Medical History, Medication, Sleep disorders and patterns and Attitudes on Wind farms.

I. Ethnicity

Back Save & Back

Ethnicity

select a participant... Remove

We are interested in your ancestry and ethnicity because we have observed that some sleep conditions are more common in people from certain parts of the world. Therefore, we would be grateful if you answer these questions as specifically as possible. If you do not know this information, just tick the option "Don't Know". If you do not wish to complete this section that is ok and will not influence your care.

Please select which group best describes your ancestry/ethnicity (based on a mixture of culture, religion, skin colour and language). If you come from a background of multiple ethnic ancestries please tick all the groups that best apply to you.

A. Caucasian - Australia/NZ (Anglo European), Europe (includes Russia Central and West Asia) & North Mediterranean, America, Canada, South Africa & Zimbabwe.
B. Indigenous Australian - Aboriginal, Torres Strait Islands.
C. Pacific Islander - New Zealand Maori or Pacific Islands, Hawaii, New Guinea.
D. South-East Asian - Brunei, Cambodia, Indonesia, Laos, Malaysia, Myanmar/Burma, Philippines, Singapore, Thailand, Vietnam.
E. South Asian - Afghanistan, Bangladesh, Bhutan, India, Maldives, Nepal, Pakistan, Sri Lanka.
F. North East Asian - China, Hong Kong, Japan, Korea, Macau, Taiwan.
G. North Asian - Mongolia, Siberia.
H. Middle Eastern, Northern African, Somali Peninsular - Algeria, Bahrain, Djibouti, Eritrea, Ethiopia, Egypt, Israel, Iran, Iraq, Jordan, Kuwait, Lebanon, Libya, Oman, Palestinian Territories, Turkey, Turkish Cypriots, Qatar, Saudi Arabia, Somalia, Syria, Tunisia, United Arab Emirates, Yemen.
I. Sub-Saharan African - Indigenous African, African American.
J. Central/South American - Central/South America.
K. Other
L. Don't Know

Ethnicity Selection

Select for YOURSELF	 A. Caucasian  B. Indigenous Australian  C. Pacific Islander  D. South-East Asian  E. South Asian  F. North East Asian  G. North Asian  H. Middle Eastern, North Africa, Somali Peninsular  I. Sub-Saharan African  J. Central/South American  K. Other (Please Specify Below)  L. Don't Know
---------------------	--

Other

if **Other**, please specify

Country of Birth

In which country were you born?

Save & Back

II. Lifestyle

Lifestyle

